#### Secondary hypotheses:

No statistical tests will be done.

#### Statistical models:

No statistical models will be applied.

#### Statistical methods:

Log-normal distributed data

The statistical analyses will be performed on the logarithmically (base 10) transformed values. Individual titers below detection limit will be set to half that limit.

Geometric mean antibody titers (GMT) and GMRs:

The antibody titers will be summarized using GMTs with two-sided 95% confidence intervals. The calculation will be done by a proc univariate analysis. GMTs and 95% confidence intervals will be obtained by exponentiation (base 10) of the logarithmically transformed antibody titer and confidence limits. Moreover the geometric mean ratios (GMR) will be provided along with the 2-sided 95% confidence intervals. GMRs will be

Doc Number: 80333235

calculated between visit 6 (one year after full vaccination) and visit 5 (one month after full vaccination).

Median, minimum, and maximum values will be obtained using original titer values.

Binary data

The evaluation at one month after the complete schedule of 4 vaccinations is expressed as the number and percentage of subjects with hSBA titer  $\geq 8$  or rSBA titer  $\geq 8$  and  $\geq 128$  at Visit 5.

These percentages will be presented along with associated two-sided 95% Clopper-Pearson confidence intervals.

# 11.4 Exploratory Objectives Analysis

Not Applicable.

# 12. EFFICACY ANALYSIS

- 12.1 Primary Objectives Analysis
- 12.2 Secondary Objectives Analysis

Not Applicable.

12.3 Exploratory Objectives Analysis

Not Applicable.

#### 13. SAFETY ANALYSIS

The analysis of safety assessments in this study will include summaries of the following categories of safety data collected for each subject:

- Vaccine exposure.
- Solicited local and systemic adverse events and indicators of solicited adverse events.
- Unsolicited adverse events

#### 13.1 Analysis of Extent of Exposure

The frequencies and percentages of subjects with vaccinations will be summarized. Data will be tabulated for the All Enrolled Set. (This corresponds to Table 14.1.1.5 in the TOC)

#### 13.1.1 Safety Completeness Analysis

#### Solicited adverse events

The safety completeness analysis on solicited adverse events aims to identify subjects who completed diary cards, irrespective of severity. The analysis will show the number of subjects with *valid data* by solicited adverse event and time point. *Valid data* in the context of the safety completeness analysis are all data entered in the diary card (including implausible values) except "Not done/unknown".

Four summaries will be produced:

- 1. The frequencies of subjects who provide diary cards and collection method (i.e., clinical visit, postal mail, any means).
- 2. For each solicited adverse event, the frequencies of subjects with *valid data* will be presented by timepoint: 30 min, 6h, days 2, 3, 4, 5, 6 and 7.
- 3. For each type of solicited adverse event (local, systemic) and indicators of solicited adverse events, such as analgesic use the frequencies of subjects *with valid data*, aggregated over time points: 30 min day 7 will be divided into: 30 min, 6h day 3, day 4 day 7, and 6h day 7.
- 4. For each solicited adverse event, the frequencies of subjects *with valid data*, aggregated over time points: 30 min Day 7 will be divided into: 30 min, 6h day 3, day 4 day 7, and 6h day 7.

For the corresponding percentages, the denominator will be the respective numbers of exposed subjects, i.e., subjects who received a vaccination and were still in-study for that time point or time interval, irrespective of whether a diary card was present or not.

# 13.2 Solicited Local and Systemic Adverse Events

For details please refer to section 7.1.1 of the protocol.

Only solicited local and systemic adverse events reported in the diary card will be analyzed. Implausible measurements will not be taken into consideration in the analysis but listed in the Appendix (see section 6.3). An overview of the collected solicited adverse events with severity indication is presented in Table 13.1.

Table 13.2-1: Overview of the Solicited Adverse Events with Severity Grading

	Reaction	Grade 0/None	Grade 1/Mild	Grade 2/Moderate	Grade 3/Severe
	Erythema	<10 mm	10-25 mm	26-50 mm	>50 mm
ਕ	Induration	<10 mm	10-25 mm	26-50 mm	>50 mm
Local	Tenderness	None	Minor light reaction to touch	Cried or protested to touch	Cried when injected limb was moved
	Change in eating habits	None	Eating less than normal for 1 - 2 feeds / meals	Missed 1 or 2 feeds / meals	Missed more than 2 feeds / meals
	Sleepiness	None	Shows an increased drowsiness	Sleeps through feeds / meals	Sleeps most of the time and it is hard to arouse him / her
Systemic	Irritability None		Requires more cuddling and is less playful than usual	More difficult to settle	Unable to console
S	Vomiting	None	1 - 2 times in 24 hours	3 - 5 times in 24 hours	6 or more times in 24 hours or requires intravenous hydration
	Diarrhea Fewer than 2 loose stools in 24 hours		2 - 3 loose stools in 24 hours	4 - 5 loose stools in 24 hours	6 or more loose stools in 24 hours or requires intravenous hydration
	Fever		Captured as No	o (<38°C) or Yes (≥38°C	)

Solicited adverse events will be reported at 30 minutes, at 6 hours on day 1 and then daily until day 7 using structured diaries. The analyses of solicited adverse events will be done separately for 30 minutes and based on three intervals: 6h - day 3, day 4 - day 7 and 6h - day 7, each without 30minutes data. In addition solicited adverse events ongoing after day 7 will be presented as unsolicited AE.

Doc Number: 80333235

For erythema and induration, recorded originally as diameters (mm), the following categorizations will be used to summarize the data for a pediatric population:

Type I: none (0 mm), any (1-9 mm, 10-25 mm, 26-50 mm, >50 mm)

Type II: Grade 0 (< 10 mm), any (10-25 mm, 26-50 mm, >50 mm)

Body temperature will be broken down by route of measurement according to the recommendations of the Brighton collaboration and will be summarized according to the 3 schemes described below:

- by 0.5 °C increments: <36.0, ≥36.0-<36.5, ≥36.5-<37.0, ≥37.0-<37.5, ≥37.5-<38.0, ≥38.0-<38.5, ≥38.5-<39.0, ≥39.0-<39.5, ≥39.5-<40.0, ≥40.0°C
- by 1.0 °C increments: <36.0, ≥36.0-<37.0, ≥37.0-<38.0, ≥38.0-<39.0, ≥39.0-<40, ≥40°C
- $<38.0, \ge38.0$  °C

Fever, defined as a body temperature of  $\ge 38^{\circ}$ C irrespective of route of measurement, will be integrated to the summaries as an indicator of a systemic adverse event.

The analyses will encompass summaries of the data on five levels:

- 1. Daily reports of subjects with solicited adverse events.
- 2. Time of first onset of solicited adverse events (excluding 30 min measurement).
- 3. Solicited adverse events, maximum event severity by event and interval (6h day 3, day 4 day 7, and 6h day 7, each without 30 min).
- 4 Duration of solicited adverse events
- 5. Solicited adverse events and indicators of solicited adverse events, occurrence of at least one event by category (local, systemic) and interval 6h-day 3, day 4- day 7 and 6h-day 7, each without 30 min.

For each of the time points or time intervals presented in the summaries, only subjects with at least one plausible observation (i.e., any non-missing values but excluding "Not done/unknown" and implausible values) for the solicited adverse events in the interval of interest will be considered. Subjects without plausible data (i.e. missing values or reported as "Not done/unknown" and implausible values) will be removed from the denominator to prevent a downward bias (towards zero).

#### Level 1: Daily reports of solicited adverse event

For each of the time points only subjects with at least one plausible observation (i.e., any non-missing values but excluding "Not done/unknown" and implausible values) for the

Doc Number: 80333235

solicited adverse event in the interval of interest will be considered. Subjects without plausible data (i.e. missing values or reported as "Not done/unknown" and implausible values) will be removed from the denominator in order to prevent a downward bias (towards zero). Data collected will be summarized (frequencies and percentages of subjects), solicited adverse event, vaccination number and time point.

#### Level 2: Time of first onset of solicited adverse events

The **time of first onset** is defined, for each subject, for each solicited adverse event, as the time point at which the respective solicited adverse event first occurred. For erythema and induration the following threshold(s) will be used:  $\geq 1$  mm,  $\geq 10$  mm. The summary will provide the frequencies and percentages of subjects with first onset of each solicited adverse events by each time point.

For each vaccination the first onset of the adverse event will be used for each subject. For any vaccination the worst adverse event across all vaccinations per time point will be used. Note, 'not done' is treated identical to 'missing'.

#### Level 3: Solicited adverse events, maximum event severity by event and interval

The **maximum event severity** will be defined if there is at least one plausible non-missing observation (excluding "Not done/unknown" and implausible values) within this time interval. Each subject's data will be aggregated across the time points of the interval and summarized according to the maximal severity observed for each adverse event, followed by a summary across subjects for each vaccine. Subjects without any solicited adverse events in the interval, i.e., missing values at each of the requested time points, will be removed from the denominator.

#### Level 4: Number of days with solicited adverse events

The number of days with the adverse event is defined irrespective of severity. This means at least 'mild' solicited adverse event that are assessed qualitatively and  $\ge 1 \text{ mm} / \ge 10$ , mm for erythema and induration. If a solicited adverse event continues beyond day 7 the period after day 7 is added.

The frequency distribution of the number of days will be provided in a summary table by adverse event.

Level 5: Solicited adverse events, occurrence of at least one event by category (local, systemic) and interval.

The occurrence of at least one solicited adverse event is defined as "any" for a subject if he/she reports greater than "none":  $\geq 1$  mm,  $\geq 10$  mm for erythema and induration) for

BCDM-14 TEMP 01 / Atlas No. 296412 Version No. 4 / Version Date: July 22, 2014 the respective event and "none" otherwise. The occurrence of at least one solicited adverse event (i.e., none versus any) will be summarized by category (i.e., local, systemic, any), by vaccination (after each vaccination and after any vaccination) and by time interval.

Medications to treat or prevent pain or fever will be summarized by frequencies and percentages of subjects reporting use of the medications by interval 30 min, 6h - day 3, day 4 - day 7, 6h - day 7.

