### 3.4 Data Collection

### 3.4.1 Data Collected from Subjects

The following data will be collected from each subject over the duration of their study participation:

• Demographic Information (Date of Birth, Sex, Weight, Height)

- Adverse Events Seriousness, Date of Onset, Date of Resolution, Frequency, Severity, Actions Taken, Outcome, Relationship to Study Vaccine
- Medical History that may be relevant to subject eligibility for study participation such as prior vaccinations
- Concomitant Medications
- Vaccination record (Pre-Vaccination Body Temperature, Date of Vaccination, Injection Site)
- Study termination (Reason(s) for ending study participation or Reason(s) for early termination)

All data collected must only be identified using the Novartis Subject ID, as described in section 5.1.4, Randomization.

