#### **Solicited Local Adverse Events**

Injection site erythema, injection site induration, injection site tenderness.

Solicited local adverse events will be collected daily by the subject(s) parent(s)/legal guardian(s) for 7 consecutive days starting from the day of each study vaccination. They will be recorded in the Subject Diary and entered into the eCRF

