#### **Other Solicited Adverse Events**

- Use of analgesics / antipyretics for treatment (Days 1-7 after each study vaccination)
- Use of analgesics / antipyretics for prophylaxis (Days 1-7 after each study vaccination)
- Body temperature (preferably tympanic)

Above listed indicators of reactogenicity will be collected daily by the subject(s) parent(s)/legal guardian(s) for 7 consecutive days starting from the day of each study vaccination. They will be recorded in the Subject Diary and entered into the eCRF.

The study staff must review the data entered into the Subject Diary as described in section 3.4.2, Tools Used for Data Collection and section 5.3.1, Follow-up Clinic Visit(s).

Note: Any solicited adverse event that meets any of the following criteria must be entered into subjects' source document (see section 9.1, Source Documentation) and also as an adverse event on the Adverse Event CRF:

- Solicited local or systemic adverse event that continues beyond day 7 after vaccination.
- Solicited local or systemic adverse event that leads to a visit to a healthcare provider (medically attended adverse event, see section 7.1.3, Evaluation of Adverse Events).

- Solicited local or systemic adverse event leading to the subject withdrawing from the study or the subject being withdrawn from the study by the investigator (adverse event leading to withdrawal, see section 7.1.3, Evaluation of Adverse Events).
- Solicited local or systemic adverse event that otherwise meets the definition of a serious adverse event (see section 7.1.4, Serious Adverse Events).

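### The SAP's ≥10 mm duration of erythema and induration takes in days after Day 7 for which no diameter measurement is described, so it can be overstated

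*SAP*

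**What the plan says.** SAP 13.2 summarises solicited events at five levels; Level 4 is duration. It states that "The number of days with the adverse event is defined irrespective of severity". It then explains that a day counts if a qualitatively assessed event is at least mild, or if erythema or induration reaches ≥1 mm or ≥10 mm. The next sentence is "If a solicited adverse event continues beyond day 7 the period after day 7 is added". It names no threshold, no required size at Day 7 and no data source.

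Four other provisions bear on it:

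- **Grading (SAP 13.2).** The second size categorisation reads "Type II: Grade 0 (< 10 mm), any (10-25 mm, 26-50 mm, >50 mm"), so a lesion of 1–9 mm is not an event at the ≥10 mm threshold.
- **Measurement schedule.** SAP 13.2 says "Solicited adverse events will be reported at 30 minutes, at 6 hours on day 1 and then daily until day 7 using structured diaries". Protocol 7.1.1 has parents collect local reactions "for 7 consecutive days starting from the day of each study vaccination".
- **After Day 7 (Protocol 7.1.1).** A "Solicited local or systemic adverse event that continues beyond day 7 after vaccination" must be entered in the source document and on the Adverse Event CRF. Protocol 3.4.1 lists the adverse event items as seriousness, then "Date of Onset, Date of Resolution, Frequency, Severity, Actions Taken, Outcome, Relationship to Study Vaccine". Protocol 7.1.3 grades CRF severity by limitation of normal daily activity.
- **Data used (SAP 13.2).** "Only solicited local and systemic adverse events reported in the diary card will be analyzed".

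**The concern.** A ≥10 mm day-count needs a diameter for each day counted. Up to Day 7 the diary supplies one. After Day 7 the described data say only that the reaction was still present and when it ended. Level 4 nevertheless adds the later period without distinguishing the ≥1 mm count, where presence is enough, from the ≥10 mm count, where it is not.

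Reactions commonly shrink before they disappear. Adding the period to resolution therefore puts days on which the lesion may have been Grade 0 into a count meant for lesions that the grading table calls at least mild. The effect falls only on reactions that outlast Day 7. The sentence also leaves room for two programmers to produce different tables from the same data.

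**Working it through.** The documents give no duration figure, lesion size or length of late reaction, so there is no stated number to reproduce. The check follows the data path and then shows, on assumed lesions, how the rule behaves.

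**Data path**

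1. Days 1–7: diameter in the diary (Protocol 7.1.1; SAP 13.2).
2. After Day 7: Adverse Event CRF with onset and resolution dates and an activity-based severity. No diameter is listed (Protocol 3.4.1, 7.1.1, 7.1.3).
3. Level 4 count: diary days at the threshold plus the period after Day 7 (SAP 13.2).

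**Direction of error**

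Let D be the diary days ≥10 mm, T the days from Day 8 to the end of the reaction, and T10 those of the T days on which the lesion is still ≥10 mm.

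- Count when the full period is added: D + T
- True count: D + T10
- Excess: T − T10, which is never negative because T10 ≤ T

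The excess is zero if the reaction ends by Day 7, or stays ≥10 mm until it ends. At ≥1 mm there is no comparable problem, provided the end date means that the lesion has gone.

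**Illustration (all sizes and rates assumed)**

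The lesion has diameter s at Day 7, shrinks linearly by g mm a day and is recorded as ended once below 1 mm. T is the number of k ≥ 1 with s − gk ≥ 1, and T10 the number with s − gk ≥ 10. The lesion is taken as ≥10 mm on all 7 diary days, so D = 7.

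| s at Day 7 (mm) | g (mm/day) | T | T10 | Rule: 7 + T | True: 7 + T10 | Excess |
|---|---|---|---|---|---|---|
| 10 | 1 | 9 | 0 | 16 | 7 | 9 |
| 10 | 2 | 4 | 0 | 11 | 7 | 4 |
| 10 | 5 | 1 | 0 | 8 | 7 | 1 |
| 12 | 1 | 11 | 2 | 18 | 9 | 9 |
| 12 | 2 | 5 | 1 | 12 | 8 | 4 |
| 12 | 5 | 2 | 0 | 9 | 7 | 2 |
| 20 | 1 | 19 | 10 | 26 | 17 | 9 |
| 20 | 2 | 9 | 5 | 16 | 12 | 4 |
| 20 | 5 | 3 | 2 | 10 | 9 | 1 |
| 30 | 1 | 29 | 20 | 36 | 27 | 9 |
| 30 | 2 | 14 | 10 | 21 | 17 | 4 |
| 30 | 5 | 5 | 4 | 12 | 11 | 1 |

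**Dependence on the meaning of 'continues'**

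Take a lesion of 9 mm at Day 7, shrinking 1 mm a day: T = 8 and T10 = 0. If the period goes to both counts whatever the Day 7 size, the ≥10 mm count gains 8 unsupported days. If the lesion must still be ≥10 mm at Day 7, it gains none. The SAP does not say which applies. For lesions ≥10 mm at Day 7, the table holds under both readings.

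**The case against.** The strongest reply is about reading. Level 4 defines the event at each threshold before it adds the later period, so for the ≥10 mm count the thing that continues should be a ≥10 mm reaction. On that reading a lesion below 10 mm at Day 7 gains nothing. This has force. A reader might infer, for example, that a lesion of 12 mm on Days 1–2 and 4 mm until Day 28 would be counted as 2 + 21 = 23 days instead of 2. That follows only if the period is added regardless of Day 7 size, which the text permits but does not state. The reply does not help a lesion that is ≥10 mm at Day 7 and shrinks later, because every day to resolution is still added.

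Other points for the plan stand in part:

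- **Missing layouts.** The diary, CRF and mock-up tables are not among the documents, and long reactions also go into source documents. It can be said only that no diameter after Day 7 is described, not that none is taken.
- **The diary-only sentence.** A reader might see a contradiction with Level 4. The sentence can equally be read as fixing which events are analysed, and a continuing reaction was already in the diary. What is missing is the name of the source for the later dates.
- **Weight.** A reader might infer that the primary tolerability result is misstated. The primary safety endpoints in Protocol 8.1.1.1 are frequencies and percentages, with solicited events limited to Days 1–7. Duration is not among them.
- **Frequency.** A reader might apply an assumed rate, say 2–5%, to the 540 planned doses (135 × 4) and arrive at about 11–27 affected reactions. The documents give no such rate. The figure would count every reaction lasting past Day 7, not only those that drop below 10 mm before they end, and would ignore the planned 25% drop-out.
- **Direction.** Overstating duration is cautious for tolerability, and stopping at Day 7 truncates reactions that stay large. The fix meets this by showing those reactions separately.

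**Conclusion.** The concern holds as a limited defect in a descriptive table. Level 4 does not separate the two thresholds when it adds the period after Day 7, and the described data cannot show on which of those days a lesion was ≥10 mm. The added period can overstate the ≥10 mm duration and cannot understate it, for reactions that outlast Day 7 and fall below 10 mm before they end.

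The number of such reactions is unknown. For the assumed lesions of 10 to 30 mm at Day 7, the excess is 9 days at 1 mm/day, 4 days at 2 mm/day and 1–2 days at 5 mm/day. These figures show how the rule behaves and do not forecast the trial's results.

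The conclusion assumes that the recorded end date is correct and that no diameter after Day 7 is collected outside the documents. Incidence, maximum severity, the listed primary safety endpoints and immunogenicity are unaffected.

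**What to change.** In SAP 13.2 Level 4:

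1. Add the period after Day 7 only to the ≥1 mm count and to the qualitatively graded events, and name the Adverse Event CRF dates as its source.
2. For the ≥10 mm count, use only diary days with a recorded diameter ≥10 mm.
3. Show reactions still ≥10 mm at the Day 7 entry in a separate category, '≥10 mm, ongoing at Day 7', so that no long reaction is hidden.

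The cost is one or two sentences and a small programming change. The downside is that the ≥10 mm duration is censored at Day 7 for a few reactions.

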#### 13.3 Unsolicited Adverse Events

The first-line analysis will use unsolicited adverse event data from all reporting sources combined. A second-line analysis will encompass the analysis of unsolicited adverse events by source (e.g. diary cards, medical records, study specific worksheet).

All the unsolicited adverse events occurring during the study, judged either as probably related, possibly related, or not related to vaccination by the investigator, will be recorded. The original verbatim terms used by investigators to identify adverse events in the CRFs will be mapped to preferred terms using the MedDRA dictionary. The unsolicited adverse events will then be grouped by MedDRA preferred terms into frequency tables according to system organ class. Adverse events judged by the investigator as at least possibly related to study vaccine will be summarized, according to system organ class and preferred term within system organ class. When an unsolicited adverse event occurs more than once for a subject, the maximal severity and strongest relationship to the vaccine group will be counted.

Only vaccine-emergent adverse events (see section 8.7 for definition) will be analyzed, i.e., excluding those after a subject has given informed consent but before vaccination. The selection of unsolicited adverse events and the assignment to time intervals will be done by day of onset and not by days ongoing/persisting.

The summaries will be presented by onset and will include frequency distributions of the different adverse events:

- Vaccination period 1: Onset between visit 1/day 1 and visit 2/day 61.
- Vaccination period 2: Onset between visit 2/day 61 and visit 3/day 121.
- Vaccination period 3: Onset between visit 3/day 121 and visit 4/day 301.
- Vaccination period 4: Onset between visit 4/day 301 and visit 6/day 661or study termination.
- Overall

The analysis of unsolicited adverse events comprises the following categories:

- Medically attended unsolicited adverse event.
- Possibly or probably related medically attended unsolicited adverse events.
- Unsolicited adverse events leading to death.
- Serious adverse events.
- Possibly or probably related serious adverse event.
- Unsolicited adverse events leading to premature withdrawal from study.
- Unsolicited adverse events leading to dose reduction, interruption or delay in study vaccination.
- Unsolicited adverse events leading to hospitalization.

Solicited adverse events continuing beyond day 7 will be coded by MedDRA and combined with the respective unsolicited adverse events.

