## **8.4.2.1.3** Analysis of Unsolicited Adverse Events

This analysis applies to all adverse events occurring during the study, judged either as probably related, possibly related, or not related to vaccination by the investigator, recorded in AE CRF, with a start date on or after the date of first vaccination. AE starting prior to the first vaccination will only be listed. The original verbatim terms used by investigators to identify adverse events in the CRFs will be mapped to preferred terms using the MedDRA dictionary. The adverse events will then be grouped by MedDRA preferred terms into frequency tables according to system organ class.

All reported adverse events, as well as adverse events judged by the investigator as at least possibly related to study vaccine, will be summarized according to system organ class and preferred term within system organ class. These summaries will be presented by vaccination group and by interval of study observation. When an adverse event occurs more than once for a subject, the maximal severity and strongest relationship to the vaccine group will be counted.

Separate summaries will be produced for the following categories:

- Serious adverse events
- Adverse events that are possibly or probably related to vaccine
- Adverse event leading to withdrawal
- Adverse events leading to a medically attended visit

Data listings of all adverse events will be provided by subject. In addition, adverse events in the categories above will be provided as listed data.

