#### 3. STUDY DESIGN

This is a Phase IV multicenter open label study planned at 6 sites. The study design has 6 clinical visits. At the first 4 visits the subjects will receive a dose of MenACWY vaccine and at visit 5 and 6 a blood draw will be taken. The subjects study participation is approximately 22 months. See also Table 3-1 for an overview of the clinical visits and Table 3-2 for the time and events.

Table 3-1: Overview of the study design

Number	Visit 1	Visit 2	Visit 3	Visit 4	Visit 5	Visit 6
of Subjects	2-Months	4-Months	6-Months	12-Months	13- Months	24- Months
135	Menveo®	Menveo®	Menveo®	Menveo®	Blood draw	Blood draw

For further details please refer to section 3.0 of the protocol.

Table 3-2: Time and Events Table – Treatment Period

Visit Type		Clinic Visit	Reminder Phone Call	Clinic Visit	Reminder Phone Call	Clinic Visit	Reminder Phone Call	Clinic Visit	Reminder Phone Call	Clinic Visit	Clinic Visit
Study Day		1	3	61	63	121	123	301	303	331	661
Days Post Injections			2 days post dose 1	60 days post dose 1	2 days post dose 2	60 days post dose 2	2 days post dose 3	180 days post dose 3	2 days post dose 4	30 days post dose 4	330 days post visit 5
Visit Window (Days)		n/a	-1/+1	+/-7	n/a	+/-7	-1/+1	+14	-1/+1	-7/+14	+/-60
Months of age		2		4		6		12		13	24
Visit Number		1		2		3		4		5	6
Study Event	References										
Study Treatment											
Vaccination	Section 5.2	X		X		X		X			
Screening and Safety											
Inform Consent *	Section 5.1.1	X a									
Medical History	Section 5.1.2	X									
Physical Exam	Section 5.1.2 and 5.3.1	X b		X		X		X		X	X
Exclusion/Inclusion Criteria	Section 4.0	X c		X		X		X		X	X
30 Minutes Post Injection Assessment	Section 5.2.1	X		X		X		X			
Subject Diary Dispensed/Training	Section 5.2.1	X		X		X		X			

Visit Type	Visit Type		Reminder Phone Call	Clinic Visit	Reminder Phone Call	Clinic Visit	Reminder Phone Call	Clinic Visit	Reminder Phone Call	Clinic Visit	Clinic Visit
Study Day		1	3	61	63	121	123	301	303	331	661
Days Post Injections			2 days post dose 1	60 days post dose 1	2 days post dose 2	60 days post dose 2	2 days post dose 3	180 days post dose 3	2 days post dose 4	30 days post dose 4	330 days post visit 5
Visit Window (Days)		n/a	-1/+1	+/-7	n/a	+/-7	-1/+1	+14	-1/+1	-7/+14	+/-60
Months of age		2		4		6		12		13	24
Visit Number		1		2		3		4		5	6
Study Event	References										
Subject Diary Reminder Call	Section 5.2.2		X		X		X		X		

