### **Unsolicited Safety Set**

The unsolicited adverse events safety set will be split into 4 periods, following each vaccination with duration until the next vaccination or study termination. The Unsolicited Adverse Events Safety Set consists of all subjects in the Exposed Set with any unsolicited adverse event data in the period of:

- Visit 1/day 1 to visit 2/day 61 (Unsolicited Safety Set Period 1)
- Visit 2/day 61 to visit 3/day 121 (Unsolicited Safety Set Period 2)
- Visit 3/day 121 to visit 4/day 301 (Unsolicited Safety Set Period 3)
- Visit 4/day 301 to visit 6/day 661 or study termination (Unsolicited Safety Set Period 4)
- Overall

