#### Unsolicited Adverse Events

All adverse events will be characterized according to the date of occurrence related to the first vaccination as follows:

- Emergence before vaccination phase: start date before the first date of injection of study vaccine.
- Emergence during vaccination phase: start date on or after the first date of injection of study vaccine or, adverse event increase in severity including to "serious" adverse event.

If start date is equal to the first date of injection then "timing" variable ("On injection day, before injection")"On injection day, after injection") will be used to define whether the adverse event occur before or after the injection.

If there are several vaccinations, the adverse event will be associated with the most recent vaccination.

If an adverse event start date is missing or unknown, the adverse event will be considered as emergent.

When start and/or end dates of an adverse event are only partially known, adverse events will be categorized as emergent before, during, or after vaccination phase using the following rules:

- If the partial end date is before (<) the first study vaccination (i.e., year or year & month is/are before the first study vaccination year or year & month) then the adverse event is emergent before vaccination phase.
- If the partial start date is equal or after (≥) the first study vaccination (i.e., year or year & month is/are after or the same as the first study injection year or year & month) then the adverse event is emergent during vaccination phase.

The **maximum event severity** is the greatest severity associated with a preferred term for a reported adverse event according to the following order: Mild < Moderate < Severe. Unknown/ Missing severity is considered as severe (except for the definition of emergence).

Doc Number: 80333235

Multiple AEs with the same PT for the same subject are counted only once.

**Vaccination-related Adverse Events** are those for which the cause has been evaluated by the investigator, and recorded as possibly related, probably related or unknown/missing.

Safety Laboratory Data

Not applicable

Previous, Concomitant and Post-Vaccination Medications

A **previous medication** is a medication used only before the first study vaccination (i.e. medication end date < first study vaccination date).

A **post-vaccination medication** is a medication used only after study termination (i.e. medication start date > study termination date).

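### The SAP's vaccination periods for unsolicited AEs last 60, 60, 180 and 360 planned days, so the figures for doses 3 and 4 are not comparable with those for doses 1 and 2

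*SAP*

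**What the plan says.** SAP V2 section 7.5 defines the periods: "The unsolicited adverse events safety set will be split into 4 periods, following each vaccination with duration until the next vaccination or study termination". Section 13.3 sets the boundaries by planned study day. The opening one reads "Vaccination period 1: Onset between visit 1/day 1 and visit 2/day 61". The next two close at the third and fourth doses, planned for days 121 and 301. The final one, with no later dose to close it, reads "Vaccination period 4: Onset between visit 4/day 301 and visit 6/day 661or study termination".

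An Overall summary is also planned. Events go to a period by day of onset. Section 8.7 sets no time limit on attribution to a dose: "If there are several vaccinations, the adverse event will be associated with the most recent vaccination". It also counts a child once per preferred term.

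The categories in section 13.3 include medically attended events, serious events, events leading to withdrawal, and related subsets of the first two. Section 13.3 speaks of frequencies; protocol section 8.1.1.1 expresses safety as frequency and percentage. Protocol section 8.4.2.1.3 asks for the by-interval display: "These summaries will be presented by vaccination group and by interval of study observation".

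Time under observation appears in SAP section 9.1 as a disposition summary only. It is not used as a denominator.

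**The concern.** The label vaccination period, together with attribution to the latest dose, invites the reader to treat the four columns as the safety profile of doses 1 to 4. The columns cover very different lengths of follow-up, and the measure is a count or percentage of children, which grows with time observed. Period 4 includes the whole interval from Visit 5 to Visit 6, when no vaccine is given.

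Two misreadings are possible. Higher figures for doses 3 and 4 could be taken as reactogenicity building up over the series. Conversely, a real excess in the weeks after dose 4 could be diluted by nearly a year of ordinary childhood illness.

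Safety and tolerability of the series is a primary objective, and the study has a single arm, so no control column shows what background alone would produce. The solicited tables avoid the problem because every dose has the same seven days.

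**Working it through.** **Period lengths.** From the study days in SAP sections 7.5 and 13.3: 61 − 1 = 60; 121 − 61 = 60; 301 − 121 = 180; 661 − 301 = 360 days. The Days Post Injections row of SAP Table 3-2 agrees: 60, 60, "180 days post dose 3", then 30 + 330 = 360. The ratio is 1 : 1 : 3 : 6.

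**Visit windows.** Periods 1 and 2 can each run 60 ± 7 = 53 to 67 days. Period 3 runs 180 to 180 + 14 = 194 days. If Visit 4 is set by age 12 months instead, period 3 is about 137 to 218 days. Period 4 runs from 30 − 7 + 330 − 60 = 293 to 30 + 14 + 330 + 60 = 434 days. The ranges for periods 1 and 2 are identical, period 3 is always longer than either, and period 4 is always longer than period 3.

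**Effect of length alone.** Assume a constant background rate, no vaccine effect and full follow-up. If p is the proportion of children with an event per 60 days, the proportion with at least one event in a period of L days is 1 − (1 − p)^(L/60). The exponents are 1, 1, 3 and 6. The documents give no value of p, so a range is shown.

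| Assumed p per 60 days | Period 1 | Period 2 | Period 3 | Period 4 |
|---|---|---|---|---|
| 1% | 1.0% | 1.0% | 3.0% | 5.9% |
| 5% | 5.0% | 5.0% | 14.3% | 26.5% |
| 10% | 10.0% | 10.0% | 27.1% | 46.9% |
| 20% | 20.0% | 20.0% | 48.8% | 73.8% |

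For example, at 20%: 1 − 0.8³ = 0.488 and 1 − 0.8⁶ = 0.738. The figures level out only if the average rate falls to 1/3 (period 3) and 1/6 (period 4) of the period 2 rate.

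**Dilution after dose 4.** Assume an independent extra 10% risk in the 30 days after dose 4.

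- With p = 20%, a 30-day figure moves from 1 − √0.8 = 10.6% to 1 − 0.9 × √0.8 = 19.5%. The period 4 figure moves from 73.8% to 1 − 0.9 × 0.8⁶ = 76.4%.
- With p = 5%, the 30-day figure moves from 2.5% to 1 − 0.9 × √0.95 = 12.3%. The period 4 figure moves from 26.5% to 1 − 0.9 × 0.95⁶ = 33.8%.

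**Early leavers.** A child with any unsolicited data in period 4 is in that period's safety set, however soon the child leaves. SAP section 5 allows about 25% drop-out over the whole study. As an extreme, place all of it evenly across period 4: the figure falls from 26.5% to 23.3% at p = 5%, and from 73.8% to 66.6% at p = 20%. Both remain above period 3 (14.3% and 48.8%).

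**What equal windows or rates give.** Under the same constant rate, a 30-day window gives 2.5% after every dose at p = 5% and 10.6% at p = 20%. A person-time rate gives 2.56 and 11.2 events per 100 child-months (30-day months) in every period, from −ln(1 − p) ÷ 60 × 30 × 100.

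**The case against.** A reader might infer that the figures must rise at every dose. The documents do not support this. Periods 1 and 2 have the same planned length, and the later rise needs a roughly constant background rate. With an assumed vaccine-linked excess falling 20%, 15%, 10% and 5% over the doses, on a 2% per 60 days background, the four figures are 21.6%, 16.7%, 15.3% and 15.8%, which is no steady rise.

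A reader might also infer that the primary safety endpoint is distorted. Protocol section 8.1.1.1 defines medically attended events, withdrawals due to events and serious events over Day 1 to Visit 6, and the Overall summary serves that definition.

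The defence has further points. The plan makes no between-dose comparison, the day boundaries are printed beside each period, and the intervals cover all follow-up as protocol section 8.4.2.1.3 asks. Nor would a signal after dose 4 disappear altogether. Solicited events have seven-day tables after each dose, events are listed by subject, and related medically attended and related serious events are separate categories. Relatedness already requires plausible timing, so the constant-background model does not describe those categories.

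All of this stands and confines the point to the by-dose tables of unsolicited events. It does not make those columns comparable. Printed boundaries are not a caution, and counts have the same length problem as percentages.

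**Conclusion.** The point holds for the by-period tables in SAP V2 section 13.3 and the sets in section 7.5. Periods 3 and 4 are three and six times as long as periods 1 and 2. At a roughly constant background rate, that alone takes an assumed 5% to 14% and 26%, or an assumed 20% to 49% and 74%. For rarer events the absolute gap is small: 1% becomes 3% and 6%. The ordering survives the visit windows and the drop-out case shown. The size depends on assumed event rates and on the rate not falling steeply with age or time since dose. This is a cheap improvement to the by-dose presentation in a single-arm study with safety as a primary objective; it does not invalidate the safety analysis.

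**What to change.** In SAP section 13.3:

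1. Keep Overall and the four period tables.
2. Add a by-dose table for each event category, by onset within one equal window after every dose. Days 1 to 30 would serve, since it fits inside the shortest permitted dose interval of 60 − 7 = 53 days. The window needs its own justification: the 30-day wording in protocol section 5.5.1 applies only to the early termination visit and is not an analysis window.
3. Add events, and children with an event, per 100 child-months at risk, by period and overall, censored at last contact.
4. Footnote the period tables with their planned lengths (60, 60, 180 and 360 days) and state that the figures are not comparable between doses.

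The cost is SAP wording and a few extra tables; onset, vaccination and termination dates are already collected. One limitation remains. After dose 3 the next planned clinic interview is 180 days later, against 60, 60 and 30 days after doses 1, 2 and 4, so events in the dose 3 window are still elicited with longer recall.
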